Appendix A: Schedule of Activities

1. **BACKGROUND**

1.1 **PATHOPHYSIOLOGY**

Retinitis Pigmentosa (RP) is the term used for a genetically heterogeneous group of inherited retinal degenerations caused by a mutation in one of the many genes which cause rod photoreceptors to die. Photoreceptors are cells in the retina that are stimulated by light, initiating the translation of visual images into nerve impulses that travel to the brain. There are two types of photoreceptors, rods and cones. Rods enable vision in dim illumination; cones are responsible for more detailed central vision, vision in bright light, and perception of color. The vast majority (95%) of photoreceptors are rods.

Rods are the major consumers of oxygen in the retina and the loss of rods causes an increase in the tissue oxygen level in the outer retina.[1] This activates NADPH oxidase causing accumulation of superoxide radicals in the cytosol [2] and also increases their generation in mitochondria of cones. The excess superoxide radicals overwhelm superoxide dismutase 1 (SOD1) and SOD2 and cause a chain reaction by which other free radicals are generated including some that are even more damaging than superoxide radicals, such as hydroxyl radicals and peroxynitrite.[3] The free radicals attack proteins, lipids, and DNA causing specific modifications that indicate that oxidative damage has occurred. The most common modification to proteins from oxidative damage is the formation of carbonyl adducts.[4, 5] Measurements of these markers of oxidative damage provide a quantitative assessment of the amount of oxidative damage that has occurred in a tissue.[6] These modifications can impair the function of macromolecules and while there are endogenous repair processes, they are overwhelmed by severe oxidative stress resulting in reduced cellular function and eventually apoptosis. After rods are eliminated from the photoreceptor layer, oxidative stress in the outer retina is severe and leads to gradual cone cell death usually starting in the midperiphery where cone density is low and then spreading peripherally and posteriorly.[7-9] The posterior spread of cone death results in visual field constriction and eventually a central island of vision and its elimination causes blindness.

Clinical signs of RP include pigmentary changes in the retina, often around blood vessels and characterized as “bone spicule-like pigmentation”, constriction of retinal vessels, and optic disc pallor. Spectral domain optical coherence tomography can show thinning of the retina in areas of photoreceptor cell loss and with segmentation the loss is seen in the outer nuclear layer. Visual field testing shows constriction of the visual fields and electroretinography shows reduced a- and b-wave amplitudes. .

1.1 STUDY RATIONALE

Retinitis Pigmentosa (RP) is a devastating eye disease and at present there are no known treatment options that can alter the rate of vision loss and eventual blindness. In a series of studies in animal models, the effects of exposing cones in the periphery of the retina to a large excess of oxygen results in progressive oxidative damage to cone photoreceptors and cone cell death.[2, 3, 7-11] Cone cell death gradually spreads from the periphery of the retina toward its center, narrowing the visual field and eventually resulting in tunnel vision. Compared to control patients, those with RP showed significant reduction in the reduced to oxidized glutathione ratio (GSH/GSSG) in aqueous humor and a significant increase in protein carbonyl content.[12] This demonstration of oxidative stress and oxidative damage in the eyes of patients with RP, suggests that oxidative damage-induced cone cell death in animal models of RP may translate to humans with RP and support the hypotheses that (1) potent antioxidants will promote cone survival and function in patients with RP and (2) aqueous GSH/GSSG ratio and carbonyl content on proteins provide useful biomarkers of disease activity in this patient population. Orally administered N-Acetylcysteine (NAC) has been found to be a particularly effective antioxidant that promotes prolonged cone survival and maintenance of cone function in a mouse model of RP.[13] Since oral and/or topical administration of NAC is feasible for long-term treatment in humans, and NAC has a good safety profile, there is good rationale to test the effect of NAC in patients with RP. The first step is to do test different dosing regimens to identify the lowest dose that is able restore aqueous GSH/GSSG ratio and reduce carbonyl adducts on aqueous proteins.

Oxidative damage has been implicated in several diseases including cystic fibrosis, chronic obstructive pulmonary disease (COPD), and Idiopathic Pulmonary Fibrosis. NAC also has a mucolytic effect which makes it particularly useful for treatment of these pulmonary diseases. The effect of oral NAC has been tested in these indications in several clinical trials providing extensive safety data. In COPD, NAC 600mg bid improves airway function and reduces the frequency of acute exacerbations.[14, 15] Doses of up to 1800mg/day have been well-tolerated in the treatment of Idiopathic Pulmonary Fibrosis.[16] Paracetamol (acetaminophen) toxicity is treated with a loading dose of 140 mg/kg NAC followed by 70 mg/kg every 4 hours for 17 doses.[17] Normal volunteers tolerated a dose of 11.2 grams NAC/day for three months without any serious undesirable effects [18] and in another study a dose of 500mg/kg/day was tolerated.[19] The most frequent adverse events associated with the oral administration of NAC are

gastrointestinal in nature and include vomiting, diarrhea, stomatitis, abdominal pain and nausea (incidence rate $\geq 1/1000$ to $< 1/100$). Hypersensitivity reactions including anaphylactic shock and anaphylactic/anaphylactoid reaction (incidence rate $< 1/10,000$), dyspnea, bronchospasm (incidence rate $\geq 1/10,000$ to $< 1/1000$), angioedema, tachycardia, urticaria, rash and pruritus (incidence rate $\geq 1/1000$ to $< 1/100$) have been reported less frequently. Finally, reports of headache, tinnitus, pyrexia, blood pressure decreased (incidence rate $\geq 1/1000$ to $< 1/100$), face edema and hemorrhage have also been collected with oral NAC. In this study, we will use NAC 600 mg effervescent tablets which are generally more pleasant and more tolerable than large capsules; however, because the formulation contains sodium, we will exclude patients with uncontrolled arterial hypertension defined as diastolic blood pressure > 95 mm Hg or systolic blood pressure > 160 mm Hg.

In patients with Idiopathic Pulmonary Fibrosis, polymorphisms within the *TOLLIP* gene were found to influence outcomes of NAC-treated patients.[20] The product of the *TOLLIP* gene, toll-interacting protein, is an inhibitory adaptor protein acting downstream of toll-like receptors, mediators of innate and adaptive immunity. The identification of the influence of *TOLLIP* polymorphisms on the effect of NAC in Idiopathic Pulmonary Fibrosis provides rationale for collecting DNA and genotyping the same SNPs in the current trial. In addition to this candidate gene genetic analysis, we plan to collect and bank patient RNA for future transcriptome analysis. The rationale for this is to identify gene expression changes that modify disease progression in RP. There is substantial variability in rate of progression among patients with RP. A patient who loses all vision early in life can have a sibling with the same mutation who maintains vision into advanced age. This suggests that modifier genes can have a major impact on cone survival. We hypothesize that level of expression of gene products that contribute to the antioxidant defense system may influence cone cell death and hence the rate of loss of visual field. It is also possible that gene expression differences may contribute to differences in response to NAC. For these reasons we plan to collect RNA from patients which will allow us to do next generation sequencing in the future to understand the transcriptome background on which our intervention has been performed. This is an ambitious undertaking that will require additional funding, but it is critical to plan for it and collect the samples as part of this protocol. Also, while it is not critical to know the pathogenic mutation in each patient for our intervention that is directed at cone survival, the rate of rod cell death influences the rate of cone cell death and it may be useful to know the underlying mutation in each of our patients. The underlying mutation may be known in some patients who enter the trial, but it is not a

requirement. In those patients for whom the pathogenic mutation is not known, we will collect DNA to enable future genotyping studies including next generation sequencing. These studies are not part of the current study and will require additional funding, but it is important to obtain and store the samples for future use.

2. OBJECTIVES

2.1 Primary Objectives

- To assess the safety and tolerability of N-acetylcysteine (NAC) in patients with RP

2.2 Secondary Objectives

- To measure the change from baseline aqueous GSH/GSSG ratio and protein carbonyl content.
- To measure change from baseline central retinal sensitivity by microperimetry.
- To measure change from baseline spectral domain optical coherence tomography (SD-OCT).
- To genotype *TOLLIP* SNPs
- To collect samples for future genotyping and transcriptome analysis.

3. STUDY DESIGN

3. DESCRIPTION OF THE STUDY

This study is a phase 1 dose escalation study with 3 cohorts, designed to assess the safety and tolerability of NAC in subjects with RP. Thirty subjects with RP will be enrolled from the clinic population of the Wilmer Eye Institute, Johns Hopkins. Informed consent will be obtained from all study subjects prior to enrollment. Each cohort will have an experimental and an exploratory arm. Subjects with RP will be enrolled in the experimental arm if they have a high carbonyl content (≥ 0.6) and a reduced GSH/GSSG ratio (≤ 3.0) in the aqueous. Subjects with RP who don't have a high carbonyl content (≥ 0.6) and a reduced GSH/GSSG ratio (≤ 3.0) but otherwise are good candidates for the study will be enrolled in the exploratory arm. The reason for this stratification is that the primary outcome is the change from baseline carbonyl content and GSH/GSSG caused by each dose of NAC and patients who have reduced chance to show improvement could skew the data and reduce the ability to identify the minimally effect dose. In a previous study, 17 of 20 patients with RP fit these criteria, so we anticipate that 8-9 subjects in each cohort will be in the experimental group. We do not want to

completely exclude RP patients who do not fit these criteria, because they may experience substantial decrease in carbonyl content and substantial increase in GSH/GSSG and their inclusion in the exploratory arm will help to determine if patients who do not fit the criteria should be excluded from the next trial, a longer trial with a functional endpoint.

Baseline testing will include: (1) detailed medical and ophthalmological history, (2) measurement of vital signs (3) slit lamp examination, (4) funduscopy examination, (5) best-corrected visual acuity (BCVA), (6) MP1 and MAIA microperimetry, (7) SD-OCT, and (8) ultrawide angle fundus photographs. One eye will be selected as the study eye and an anterior chamber tap will be done for measurement of GSH/GSSG and protein carbonyl content. Serum GSH/GSSG, protein carbonyl content and bilirubin levels will also be measured. Blood will be obtained for RNA and DNA samples. The following is the dosing of NAC 600 mg effervescent tablets in each cohort.

	Baseline	Week 4	Week 8	Week 12	Week 20	Week 24
Cohort 1	600mg bid	600mg bid	600mg bid	600mg tid	600mg tid	600mg tid
Cohort 2	1200mg bid	1200mg bid	1200mg bid	1200mg tid	1200mg tid	1200mg tid
Cohort 3	1800mg bid	1800mg bid	1800mg bid	1800mg tid	1800mg tid	1800mg tid

There will be 8 study visits (screening, baseline and month 1-6), all study visits after the baseline visit will be 28±7 days apart, followed by a 12 week observation period. At each visit, patients will have medical history, measurement of vital signs (blood pressure, heart rate, respiratory rate and temperature), review of concomitant medications, review of study drug diary, recording of adverse events, BCVA, eye examination, and anterior chamber tap. MP1 microperimetry will be done at screening and baseline visit. Optical Coherence tomography will be done at the screening and baseline visit and repeated every 3 months. MAIA microperimetry will be done at screening and baseline visit and repeated every month. Fundus autofluorescence and Ultrawide field fundus photographs will be obtained at screening and month 6 visit. At all visits where needed, microperimetry will be performed first followed by OCT, FAF and UWFP. Serum levels of NAC pre- and post-dose will be measured at baseline, week 12 and 24. When all 10 subjects in cohort 1 have had a week 4 visit, the PI will review safety and tolerability with study team members and if there has been good safety and tolerability, enrollment will begin for cohort 2. When all 10 subjects in cohort 2 have had a week 4 visit, the PI will

review safety and tolerability with study team members and if there has been good safety and tolerability, enrollment will begin for cohort 3.

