3.3 SAFETY PLAN

The safety assessments to be conducted for this study are listed in Section 5

Potential safety issues are associated with anterior chamber taps and peripheral blood draw. Subjects will be instructed to contact their physician at any time should they have health-related concerns. All adverse events (serious and non-serious) will be recorded for up to 14 days after the last study visit.

Anterior chamber tap in the clinic in patients with RP

The patient will be seated at a slit lamp and a drop of topical anesthetic will be placed in the study eye. A 30 gauge needle will be passed through the limbus into the anterior chamber and 0.15 ml of aqueous humor will be removed. There are no nerves at the limbus below the epithelium and therefore the topical anesthetic provides complete anesthesia and there is no pain associated with the procedure. Anterior chamber tap is a routine procedure that is extremely safe. It is done to deal with severe

increased intraocular pressure after intravitreal injections, or injection of gas during pneumatic retinopexy. Anterior chamber taps have been done as part of several prior studies and there have been no related complications or adverse events.

Peripheral blood draw

The peripheral blood will be drawn to collect RNA and DNA samples and serum bilirubin levels at the screening visit (BL-28 to 56 days). Blood draw for measurement of serum carbonyl content and GSH/GSSG ratio will be performed at each study visit. At the baseline (Day 1 +7days), week 12 and week 24 visit, peripheral blood will be drawn before as well as 1 and 2 hours after administration of oral NAC in the clinic for measurement of plasma NAC levels. The 2 hour blood draw will be optional, based on the convenience of the subject and at the discretion of the investigator. The peripheral blood draw is commonplace procedure and there are no risks to exposure to transmissible diseases if ones blood is being drawn using aseptic conditions. A patient may feel light headed or faint, or experience pain or discomfort at the site of puncture during the procedure. There may be possible bruising or swelling at the puncture site, rarely there may be an infection.

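### Does Section 3's paragraph on baseline testing leave open which aqueous tap is the reference for change from baseline?

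*Combined protocol and SAP*

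**What the plan says.** Section 3 sorts patients by their aqueous markers. They "will be enrolled in the experimental arm if they have a high carbonyl content (≥ 0.6") together with a GSH/GSSG ratio of 3.0 or less, and otherwise they join the exploratory arm. Dose depends on cohort, not arm. The exploratory arm has a stated purpose: "their inclusion in the exploratory arm will help to determine if patients who do not fit the criteria should be excluded" from the next trial.

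The next paragraph opens "Baseline testing will include: (1) detailed medical and ophthalmological history" and its numbered list ends "7) SD-OCT, and (8) ultrawide angle fundus photographs". It then says "One eye will be selected as the study eye and an anterior chamber tap will be done", and adds serum markers: "protein carbonyl content and bilirubin levels will also be measured. Blood will be obtained for RNA and DNA samples".

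Other places give the timing of these items. Later in Section 3: "Fundus autofluorescence and Ultrawide field fundus photographs will be obtained at screening and month 6 visit". Section 3.3 has blood drawn "to collect RNA and DNA samples and serum bilirubin levels at the screening visit (BL-28 to 56 days"). Section 4.2 and Appendix A agree, and both schedule one aqueous tap at screening and another on Day 1, the visit they call baseline. Sections 3.2.2 and 4.5.2 define the marker outcomes as change from baseline and do not name a tap.

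**The concern.** The baseline-testing paragraph reads like the screening visit. Its photographs, bilirubin and RNA/DNA samples are not Day 1 procedures, and it omits plasma NAC, which is. It also mentions one tap directly after the arm cut-offs. A reader could conclude that this one tap both assigns the arm and anchors the change score.

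That double use would matter. Patients selected for high carbonyl on a noisy measurement tend to read lower next time, and those who missed the cut-off tend to read higher. The experimental arm would seem to benefit and the exploratory arm to worsen with no drug effect, which could mislead the decision on whom to exclude from the next trial. Separately, two possible references would let an analyst choose between them after seeing the data.

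**Working it through.** **1. The passages side by side**

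| Place | What it says about baseline |
|---|---|
| Section 3, baseline-testing paragraph | Pre-treatment procedures in one list; one undated tap; leads into a dosing table whose first column, Baseline, holds the starting dose |
| Section 3, next paragraph | Screening and baseline counted as separate visits; a tap at each visit; pre- and post-dose NAC levels at baseline |
| Section 3.3 | Baseline dated to Day 1; screening 28 to 56 days earlier |
| Section 4.2 | Day 1 visit headed as baseline; its tap listed before the first dose |
| Appendix A | Day 1 column headed BL; taps marked at screening and at BL |

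The paragraph does not match screening exactly either: fundus autofluorescence, a screening procedure, is missing from it. It is best read as a loose summary of the work-up over both pre-treatment visits. Everywhere else baseline is the visit at which dosing starts.

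**2. The plan's power figure**

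Section 4.5.3 states 89% power for n = 30, SD 0.8, two-sided 0.05, paired t-test. Taking the 50% difference as 0.5 in the same units (an assumption), the noncentrality is 0.5/0.8 × √30 = 3.42 and power is 91.1%. At n = 28 it is 89.0%. The formula does not depend on which tap is the reference, so the small mismatch has no bearing here.

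**3. Size if one tap did both jobs**

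Inputs: 17 of 20 earlier patients met the cut-offs (Section 3), so 85%, or 30 × 0.85 = 25.5 experimental and 4 or 5 exploratory patients. SD of the paired difference 0.8 (Section 4.5.3), taken as all measurement noise. Visit-to-visit correlation ρ is not in the documents; 0.5 to 0.8 is assumed.

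Single-visit SD = 0.8/√(2(1−ρ)). Spurious change = (1−ρ) × selection excess × SD = excess × 0.8 × √((1−ρ)/2).

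- Selection on carbonyl alone: excess 0.274 SD (experimental) and 0.274 × 0.85/0.15 = 1.554 SD (exploratory, opposite direction). At ρ = 0.5: 0.274 × 0.8 × 0.5 = 0.11 fall and 1.554 × 0.8 × 0.5 = 0.62 rise.
- Two uncorrelated markers: excess 0.159 and 0.895. At ρ = 0.8: 0.159 × 0.8 × 0.316 = 0.04 fall and 0.895 × 0.8 × 0.316 = 0.23 rise.
- A lognormal version, by simulation: fall of 0.01 to 0.06, rise of 0.07 to 0.33.

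Standard errors: exploratory arm 0.8/√5 = 0.36 to 0.8/√4 = 0.40; between arms 0.8 × √(1/25 + 1/5) = 0.39 to 0.8 × √(1/26 + 1/4) = 0.43. The lognormal gap between arms, 0.09 to 0.39, does not exceed its standard error. The normal gap, 0.27 to 0.73, can.

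Over all 30 the shifts cancel: 0.85 × 0.11 = 0.15 × 0.62 = 0.093.

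**4. With the Day 1 tap as reference and the screening tap assigning the arm**

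The shift is zero if errors are independent between visits. With autocorrelation of 0.3 to 0.5 per 28 days (assumed) and a normal model, the Week 12 residue is at most -0.05 and +0.29 for taps 28 days apart, and -0.03 and +0.14 for taps 56 days apart. Rewording the plan would not remove that residue.

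**5. Averaging the two taps**

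If 0.8 is all noise, one tap has variance 0.64/2 = 0.32. The change from a two-tap mean then has SD √(0.32 + 0.16) = 0.69 and power of 96.8%. This gain rests on the all-noise assumption. Averaging would also give the pooled analysis a different reference from the arm-level summaries, or else bring a screening tap that had assigned the arm back into the arm-level reference.

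**The case for a change.** The strongest case for acting is that no passage names the tap that assigns the arm, and Section 4.5.2 does not name the reference. If the Day 1 tap assigned the arm, the double use would arise even with Day 1 as baseline. The exploratory arm informs a real decision, and a clarifying sentence costs nothing. Simulation of the pooled paired test shows screening and Day 1 references disagreeing on significance in 9 to 12% of trials at a true change of 0.5. Under no effect, taking whichever is significant raises the error from 5% to 8 to 9%. Section 3, when explaining the arms, even calls the marker change the primary outcome, although Sections 3.2.1 and 4.5.1 make it safety.

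The silence about the assigning tap stands. Screening is the natural choice, since patients are enrolled into an arm and the screening tap precedes Day 1 by 28 to 56 days, but that is an inference. The eligibility row in Appendix A does not settle it, because Sections 4.1.2 and 4.1.3 contain no marker cut-off. The disagreement and error figures are what any two noisy references would produce, and they require an analyst to set aside a visit the protocol names and dates as baseline. Treating marker change as primary would not alter the pooled result, which is unbiased with either tap. Within the experimental arm every cohort has the same cut-offs, so comparisons between doses are largely protected.

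**Conclusion.** No change is needed. The baseline-testing paragraph is a clerical slip in a summary, and the unnamed reference tap is a gap that analysts will fill correctly: baseline is the Day 1 visit, its tap is listed before the first dose, and the outcomes are timed from the start of NAC. On that reading the pooled analysis of 30 is unbiased, the safety outcome is unaffected, and no specified test depends on the arm.

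What remains is an informal look at 4 or 5 exploratory patients. Even if one tap did both jobs, the lognormal shift of at most +0.33 in that arm is below its standard error of 0.36 to 0.40. The normal model's +0.62, its largest value, would exceed that standard error, so anyone reading the arms separately should know which tap assigned them. All these sizes are for carbonyl and assume 0.5 as the target, 0.8 as pure noise, 85% qualifying and ρ of 0.5 to 0.8; the documents give no reliability, and GSH/GSSG was not sized. A two-tap baseline is not a clear improvement.

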3.2.2 Secondary Outcome Measures

- Change from baseline aqueous and serum carbonyl content and GSH/GSSG ratio at 1, 2, 3, 4, 5, 6, 7, 8 and 9 months after initiation of NAC.
- Change from baseline BCVA 6 months after initiation of NAC.
- Change from baseline central retinal sensitivity by microperimetry 3, 6, and 9 months after initiation of NAC.
- Change from baseline ellipsoid zone (EZ) width by SD-OCT 6 month after initiation of NAC .

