3.4 COMPLIANCE WITH LAWS AND REGULATIONS

This study will be conducted in accordance with current U.S. Food and Drug Administration (FDA) Good Clinical Practices (GCPs), and local ethical and legal requirements.

4. **MATERIALS AND METHODS**

4.1 **SUBJECTS**

4.1.1 **Subject Selection**

Thirty eligible subjects with RP will be enrolled. Subjects will be identified and recruited through the clinic population at the Wilmer Eye Institute and it is expected that enrollment will be completed over an 12 month period.

4.1.2 **Inclusion Criteria**

All subjects must meet the following criteria to be eligible for study entry:

- Signed informed consent and authorization of use and disclosure of protected health information
- Age ≥ 18 years
- Patients diagnosed with RP by the investigators, based on clinical phenotype and diagnostic tests

4.1.3 **Exclusion Criteria**

Subjects who meet any of the following criteria will be ineligible for study entry:

- Patients with concurrent retinal pathologies that result in vision loss, including but not limited to retinal vein occlusion, diabetic retinopathy and neovascular age-related macular degeneration. If one eye does not have any retinal pathology other than RP, it may be enrolled in the study.
- Patients with uncontrolled arterial hypertension defined as diastolic blood pressure > 95 mm Hg or systolic blood pressure > 160 mm Hg despite medical therapy.

4.2 **STUDY ASSESSMENTS**

For a complete overview of the study assessments, see Flow Charts in Appendix section.

Screening Visit

- Obtain Informed Consent
- Record demographics, medical and ocular history; concomitant medications, smoking history, alcohol intake and supplement usage

- Vital sign measurements (blood pressure, pulse rate, temperature and respiratory rate)
- Slit lamp examination
- Indirect Ophthalmoscopy
- BCVA by Early Treatment Diabetic Retinopathy Study (ETDRS) Protocol
- SD-OCT
- Fundus autofluorescence
- Ultrawide field fundus photography
- MP1 and MAIA microperimetry
- Anterior chamber tap (for measurement of carbonyl content and GSH/GSSG)
- Blood draw for RNA and DNA samples, serum carbonyl content, GSH/GSSG ratio and bilirubin levels.

Baseline Visit (Day 1)

- Record any change in medical and ocular history; concomitant medications, smoking history, alcohol intake, supplement usage and adverse events
- Vital sign measurements (blood pressure, pulse rate, temperature and respiratory rate)
- Slit lamp examination
- Indirect Ophthalmoscopy

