- BCVA by Early Treatment Diabetic Retinopathy Study (ETDRS) Protocol
- SD-OCT
- MP1 and MAIA microperimetry
- Anterior chamber tap (for measurement of carbonyl content and GSH/GSSG)
- Obtain blood for serum carbonyl content, GSH/GSSG ratio and blood for plasma NAC Levels (before and after drug administration).
- Initiation of NAC treatment, first dose of NAC to be administered in the clinic

Four Week Visit (Week 4/ 28±7days)

- Record any change in medical and ocular history; concomitant medications, smoking history, alcohol intake, supplement usage and adverse events
- Vital sign measurements (blood pressure, pulse rate, temperature and respiratory rate)

- Slit lamp examination
- Indirect Ophthalmoscopy
- BCVA
- MAIA microperimetry
- Anterior chamber tap (for measurement of carbonyl content and GSH/GSSG)
- Blood Draw for serum carbonyl content and GSH/GSSG ratio

Eight Week Visit (Week 8/ 56±7days)

- Record any change in medical and ocular history; concomitant medications, smoking history, alcohol intake, supplement usage and adverse events
- Vital sign measurements (blood pressure, pulse rate, temperature and respiratory rate)
- Slit lamp examination
- Indirect Ophthalmoscopy
- BCVA
- MAIA microperimetry
- Anterior chamber tap (for measurement of carbonyl content and GSH/GSSG)
- Blood Draw for serum carbonyl content and GSH/GSSG ratio

Twelve Week Visit (Week 12/ 84±7days)

- Record any change in medical and ocular history; concomitant medications, smoking history, alcohol intake, supplement usage and adverse events
- Vital sign measurements (blood pressure, pulse rate, temperature and respiratory rate)
- Slit lamp examination
- Indirect Ophthalmoscopy
- BCVA
- SD-OCT
- MAIA microperimetry
- Anterior chamber tap (for measurement of carbonyl content and GSH/GSSG)
- Obtain blood for serum carbonyl content, GSH/GSSG ratio and blood for plasma NAC levels (before and after drug administration).

- NAC to be administered in the clinic

Sixteen Week Visit (Week 16/ 112±7days)

- Record any change in medical and ocular history; concomitant medications, smoking history, alcohol intake, supplement usage and adverse events
- Vital sign measurements (blood pressure, pulse rate, temperature and respiratory rate)
- Slit lamp examination
- Indirect Ophthalmoscopy
- BCVA
- MAIA microperimetry
- Anterior chamber tap (for measurement of carbonyl content and GSH/GSSG)
- Blood Draw for serum carbonyl content and GSH/GSSG ratio

Twenty Week Visit (Week 20/ 140±7days)

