4.5.2 Secondary Analysis

To measure the change from baseline aqueous and serum carbonyl content and GSH/GSSG ratio at 1, 2, 3, 4, 5, 6, 7, 8 and 9 months after initiation of NAC treatment and correlate it with changes in BCVA, retinal sensitivity, and ellipsoid zone (EZ) width.

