4.5.3 Power Analysis

Power analysis was conducted and a sample size of 30 was found to achieve 89% power to detect a mean of paired difference of 50% in aqueous carbonyl content with an estimated standard deviation of 0.8 and with significance level of 0.05 (95% confidence interval) using a 2 sided paired t-test.

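### SD-OCT is done twice before any drug, but the plan gives the screening scan no role; a Day 1-only baseline gives EZ-width change up to one third more error variance than the mean of both scans.

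*Combined protocol and SAP*

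**What the plan says.** Section 3 (Description of the Study) sets the imaging schedule: "Optical Coherence tomography will be done at the screening and baseline visit and repeated every 3 months". The visit lists in 4.2 and the schedule in Appendix A agree, with SD-OCT at screening, Day 1, and weeks 12, 24 and 36. Section 3.3 places screening 28 to 56 days before baseline. The last item listed for the Day 1 visit in 4.2 is "Initiation of NAC treatment, first dose of NAC to be administered in the clinic", so both scans appear to precede drug.

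The outcome in 3.2.2 is "Change from baseline ellipsoid zone (EZ) width by SD-OCT 6 month after initiation of NAC". The only EZ analysis in 4.5.2 is to take the biomarker change and "correlate it with changes in BCVA, retinal sensitivity, and ellipsoid zone (EZ) width". Neither section says which pre-drug scan, or which combination of scans, supplies the baseline EZ width. No section gives the screening scan a role in the analysis.

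**The concern.** Day 1 is a named baseline visit, separate from screening, so an analyst would most likely subtract the Day 1 value and leave the screening scan unused. That discards a second pre-drug measurement that is already scheduled. EZ width is the only structural outcome in 3.2.2. With 30 subjects and a 6-month interval, avoidable error in the baseline widens the interval around the mean change and weakens the correlation with the biomarkers. Leaving the rule open also lets the choice between two scans be made after the data are seen.

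EZ width suits averaging better than the other repeated measures do. It is read from an image, so practice effects of the kind that can affect visual acuity and microperimetry are not a reason against it. It also plays no part in assigning subjects to the experimental or exploratory arm. Aqueous carbonyl content and GSH/GSSG do, so averaging those would raise a selection issue that does not arise here.

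**Working it through.** **The plan's own figure.** The documents give no power, SD or repeatability for EZ width. The one power statement, "a sample size of 30 was found to achieve 89% power to detect a mean of paired difference of 50% in aqueous carbonyl content", concerns another outcome. Reading the difference as 0.5 with SD 0.8, an exact two-sided paired t-test at n = 30 gives 91.1% against the stated 89%; an SD of 0.83, which rounds to 0.8, gives 89.0%. Nothing below depends on it.

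**Inputs from the documents.** Two pre-drug scans, S (screening) and B (Day 1), 28 to 56 days apart; one follow-up scan F at week 24 (168 days).

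**Assumption.** Each scan has error variance s², with independent errors.

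- Day 1 only: Var(F − B) = s² + s² = 2s².
- Mean of both: Var(F − (S + B)/2) = s² + s²/2 = 1.5s².
- Ratio: 2/1.5 = 1.333, so the single scan carries 33% more error variance. The error SD ratio is √1.333 = 1.155, or 15% more. Put the other way, averaging removes 25% of the error variance. A simulation with one million draws gave a ratio of 1.335.

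**If the two pre-drug errors correlate (ρ).** The error variance with the mean is s²[1 + (1 + ρ)/2], so the excess for the single scan is 2/[1 + (1 + ρ)/2] − 1.

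| ρ | Excess error variance |
|---|---|
| 0 | 33% |
| 0.25 | 23% |
| 0.5 | 14% |
| 0.75 | 7% |

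**If true change varies between subjects, with variance k·s².** The excess in total variance of change is (2 + k)/(1.5 + k) − 1. This holds k the same for both baselines; if pre-drug slopes differ between eyes, the untreated weeks add some variance of their own.

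| k | Excess total variance |
|---|---|
| 0 | 33% |
| 0.5 | 25% |
| 1 | 20% |
| 2 | 14% |
| 4 | 9% |

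**Effect on the correlation in 4.5.2.** EZ error attenuates the correlation by √[k/(k + error)], where error is 2 or 1.5. With k = 1 as an example, the factor is √(1/3) = 0.58 for Day 1 only and √(1/2.5) = 0.63 for the mean. A shift in reference date that is the same for all eyes does not alter a correlation.

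**Shift of the reference date.** The mean of two scans refers to their midpoint, 28/2 = 14 to 56/2 = 28 days before Day 1. Under a steady slope this adds 14/168 = 8% to 28/168 = 17% of the 168-day change.

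**The case against.** **The plan does not say that one scan is used.** This stands. A reader might infer that the plan specifies Day 1 alone, but it leaves baseline EZ width undefined. The baseline testing listed in section 3 ends with "7) SD-OCT, and (8) ultrawide angle fundus photographs", and Appendix A places those photographs at screening and week 24, not Day 1. So the word baseline is used there more broadly than the Day 1 visit. Day 1 alone is the natural reading, not a stated rule. The remedy is needed on either reading.

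**Day 1 before dosing is a legitimate convention.** True; using it would not be an error. The case for averaging is precision at almost no cost.

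**The size is unknown.** This also stands. One third is a ceiling. A reader might suppose that measurement error dominates a 6-month change, but the documents give no repeatability, SD or progression rate to support that. The entry criteria do not require a measurable EZ width, so the number of eyes that contribute is also unknown.

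**Averaging brings untreated time into the change.** This stands as a named downside. Dividing by days since the midpoint may look like a cure, but it works only if the slope is the same before and after NAC. If NAC halted progression completely, the scaled estimate would still show 14/182 = 8% to 28/196 = 14% of the untreated rate. It would also replace the stated outcome, a change at 6 months after drug start, with a rate from an earlier date. In 4.5.2, an averaged EZ baseline paired with Day 1 biomarker baselines means slightly different windows; this should be stated.

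**Conclusion.** The point holds as a modest improvement in precision for a secondary outcome of a phase 1 safety study. Two pre-drug scans exist, the first has no stated use, and a Day 1-only baseline would carry up to one third more error variance in the change (error SD up to 15% higher) than the mean of both. The bound assumes independent, equal errors. The advantage shrinks with correlated errors or real variation between subjects, and the documents do not allow the actual gain to be sized.

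A reader might turn the bound into power: for a true change of 0.5 SD with 30 eyes, a one-sample t-test would go from 75% to 86%, as if there were 30 × 4/3 = 40 eyes. Those figures are illustrative only. The plan states no such test or effect size for EZ width, and they need the change to be entirely measurement error with all 30 eyes readable. They should not be presented as properties of this plan. No stated conclusion of the trial depends on this choice.

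**What to change.** In 3.2.2, for EZ width only, add: *Baseline EZ width is the mean of the screening and Day 1 values; if only one is readable, that value is used.* State that this baseline serves both the 6-month change and the correlation in 4.5.2, and that the change from Day 1 alone is reported as a sensitivity analysis. Keep Day 1 as baseline for visual acuity, MAIA microperimetry and the biomarkers. Do not convert the change to a per-day rate.

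The cost is a few sentences in 3.2.2 and 4.5.2 and one extra line in the results; no scan, visit or subject burden is added. The 14 to 28 day shift in reference date should be disclosed with the result, and the Day 1-only analysis shows its effect on the mean change. The rule should be fixed before EZ data are examined.
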